2.3 DETERMINATION OF SAMPLE SIZE

A target enrollment of 80 patients was chosen to allow for a projected 10–15% dropout rate and exclusion of growth data for an estimated 10% of patients who might enter puberty during the study period and leave sufficient patient numbers to compare to previous studies of immunogenicity. This target enrollment was based on enrollment in a previous study (L0368) which planned to enroll 60 patients for the assessment of growth rate and change in height standard deviation score (SDS). An initial sample size was chosen to ensure that at least 50 patients would complete the study (L0368 FR 30SEP97; Sec 4.8.4).

This study is expected to yield a minimum of 50 evaluable patients. Given a sample size of 50, and an assumed 50% of patients developing anti-GH antibodies, the 95% confidence interval (CI) around this proportion will be (35.53%, 64.47%). This interval was calculated using Clopper-Pearson methodology. Fluctuations in the proportion of patients developing anti-GH antibodies and the increase of evaluable patients will result in more precise confidence intervals. The exact confidence intervals for the scenarios for sample size of 50 and 60 in combination with the proportion of patients who are anti-GH antibody positive of 50% and 20% are listed in Table 1.

Nutropin AQ (Somatropin [rDNA origin])—Genentech, Inc. 5/Statistical Analysis Plan ML29543

Table 1

N	Proportion of Patients Who Are Anti-GH Antibody Positive	95% Confidence Interval (Lower Limit)	95% Confidence Interval (Upper Limit)
50	0.5	0.3553	0.6447
60	0.5	0.3681	0.6319
50	0.2	0.1003	0.3372
60	0.2	0.1078	0.3230

Clopper-Pearson 95% Confidence Intervals for the Proportion of Patients Who Are Anti-GH Antibody Positive Based on 50 and 60 Patients

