4.4.1 Primary Outcomes Endpoint

The primary endpoint for this study is the proportion of patients who develop anti-GH antibodies (i.e., with positive anti-GH antibody screening assay result) after initiating treatment with Nutropin AQ v1.1.

Among all patients with at least one post-baseline screening assay result, the number and percentage of patients who have at least one positive anti-GH antibody screening assay result at any post-baseline visit will be presented. The Clopper-Pearson exact 95% Cls for the percentage will also be provided.

An anti-GH antibody screening assay result is considered positive if the titer is \geq 1.0 mg/L.

4.4.2 Secondary Outcomes Endpoints

The secondary endpoints for this study are as follows:

- Proportion of patients who exhibit growth attenuation is defined as
 - (1) initial growth response greater than pretreatment velocity followed by reduction in growth response to below the pretreatment velocity in the subsequent 6- to 12month treatment period

or

(2) reaching \leq 2 cm per year at any scheduled visit: Month 3, 6, 9, or 12

Please note that for criteria (1), the initial growth response occurs as early as Month 3 and growth attenuation status at post-baseline visit will be evaluated at Months 6, 9, or 12.

The growth response is based on the annualized growth velocity defined as (height - baseline height)/ (date of height assessment – date of baseline)*365.25 at any post-baseline visit.

Pretreatment growth velocity is defined as (Baseline height – last historical height) / (date of baseline – date of last historical height)*365.25

Growth attenuation status at post-baseline visit Tk (=Month 6, Month 9 or Month 12 for k=6, 9, or 12) will be classified as follows:

Yes: If growth velocity at Tk< pretreatment growth velocity and there is Tj < Tk with growth velocity at Tj > pre-treatment growth velocity, for j<k, and k=6, 9, or 12 or growth velocity \leq 2 cm per year at any scheduled visit: Month 3, 6, 9, or 12 **No:** Otherwise.

Nutropin AQ (Somatropin [rDNA origin])—Genentech, Inc. 9/Statistical Analysis Plan ML29543 • 2x2 cross tabulation (with frequencies and percentages) of growth attenuation status (yes or no) and anti-GH antibody status (positive or negative) will be provided for each antibody assay at each visit (Month 6, 9, and12).

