Appendix 3 Programming Codes for Statistical Analysis

Programming of the tables, listings and figures will be performed using SAS Version 9.4, running under UNIX environment. The following table presents the SAS code for the efficacy analysis.

Endpoint	Test	SAS Code
95% Clopper- Pearson confidence interval	95% confidence interval for response rate	<pre>ods listing close; proc freq data = xxx; ods output BinomialCLs=CI BinomialProp=prop; table resp / binomial(level = 1 exact) out=freq1 (keep=resp count); run; ods listing;</pre>

The following macros will be used for reference to calculate the normal height SDS (zscores) for this study.

```
************
*** PROGRAM: htz.sas Macro
***
*** DESCRIPTION:
***
      Macro calculates normal height SDS (z-scores) for NCGS
***
      (Growth Hormone marketed product observational study)
***
      http://www.cdc.gov/nchs/nhanes/growthcharts/datafiles.htm
***
       was http://www.cdc.gov/nchs/about/major/nhanes/growthcharts/datafiles.htm
***
*** ASSUMPTIONS:
***
      The macro only uses formats htzml, htzfl, htzmm,
* * *
      htzfm, htzms, and htzfs in /NCGS/lib/formats.sct01.
***
      A value is returned only if sex=1 or 2, age>=0,
***
      ht>0, and the returned value is -10=<htz<=4. It
***
      uses (and drops) variables beginning with "xzzyww".
***
      ("Table" below refers fo values returned from formats.)
***
       Temporary variables used:
***
      xzzywwa age(months) in table row just less or = to input age
***
      xzzywwa2 age(months) in table row just greater than input age
***
      xzzywwi interpolation factor of age between xzzywwa and xzzywwa2
***
      xzzywwl Box-Cox transformation power in xzzywwa row
***
      xzzywwl2 Box-Cox transformation power
                                                 in xzzywwa2 row
***
      xzzywwl Box-Cox transformation power interpolated
***
      xzzywwm median
                                                 in xzzywwa row
***
      xzzywwm2 median
                                                  in xzzywwa2 row
***
      xzzywwm median interpolated
***
      xzzywws generalized coefficient of variation in xzzywwa row
***
      xzzywws2 generalized coefficient of variation in xzzywwa2 row
***
      xzzywws generalized coefficient of variation interpolated
***
*** INSTRUCTIONS FOR USER:
***
     Include the following code with your variables assigned
***
     to each of the 4 parameters.
***
     %htz(sex=,age=,ht=,htz=) ;
*** INPUT VARIABLES:
***

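### The Appendix 3 code picks the level for the primary exact interval by table position while the coding of RESP is undefined, so it can return the interval for antibody-negative patients, and does so under any coding when nobody is positive

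*SAP*

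**What the plan says.** SAP 4.4.1 defines the primary result as the "number and percentage of patients who have at least one positive anti-GH antibody screening assay result at any post-baseline visit", out of patients with at least one post-baseline screening result, with an exact Clopper-Pearson 95% interval for that percentage. It is the only Clopper-Pearson analysis in the SAP. SAP section 4 plans no hypothesis tests.

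Appendix 3 specifies SAS 9.4 and presents its code as the code for the efficacy analysis. The entry is labelled "95% confidence interval for response rate". The procedure call is "proc freq data = xxx", with a placeholder dataset name, and the table request is "table resp / binomial(level = 1 exact". There is no ORDER= option, no quoted level value and no WEIGHT statement with ZEROS. How RESP is coded is not given in Appendix 3 or elsewhere in the SAP. SAP 4.4.2 describes its statuses as positive or negative and as yes or no, but does not tie either pair to RESP.

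**The concern.** A program for a binomial interval has to identify the event. This one does so only through the sort order of a variable that the SAP does not define. A programmer who reads `level = 1` as the value 1, codes positives as 1 and negatives as 0, and runs the line as printed gets the interval for the negatives.

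The interval is the only inferential statement attached to the primary endpoint. At stake is whether it describes the proportion that 4.4.1 defines or that proportion's complement.

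**Working it through.** **Inputs.** The event, the denominator and the interval method come from SAP 4.4.1, and the code from Appendix 3. The planning cases (50 and 60 patients; 50% and 20% positive) come from SAP 2.3 and its Table 1. The counts 14/72 and 0/80 are illustrations, not figures from the documents; 80 is the enrolment target.

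**Assumption about the software.** Two facts about PROC FREQ are general SAS knowledge and are not in the SAP. An unquoted LEVEL= number is a position in the one-way table, whereas a quoted string is a formatted value. Default ordering sorts by internal value. SAS was not run; the selection was emulated by sorting the distinct values of RESP and taking the first.

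**Formula.** For x events in n, the lower limit is the 0.025 quantile of Beta(x, n−x+1) and the upper limit is the 0.975 quantile of Beta(x+1, n−x). The lower limit is 0 when x = 0 and the upper limit is 1 when x = n.

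**Step 1: reproduce Table 1.**
- 25/50: 0.3553 to 0.6447, as printed.
- 30/60: 0.3681 to 0.6319, as printed.
- 10/50: 0.1003 to 0.3372, as printed.
- 12/60: 0.1078 to 0.3233. The SAP prints 0.3230 for the upper limit, a trivial difference that has no bearing here.

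**Step 2: which level the code picks, with 10/50 positive.**

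| Coding (positive / negative) | First level in table | Interval returned |
|---|---|---|
| 1 / 0 | negative | 0.6628 to 0.8997 |
| Y / N | negative | 0.6628 to 0.8997 |
| Positive / Negative | negative | 0.6628 to 0.8997 |
| POS / NEG | negative | 0.6628 to 0.8997 |
| 1 / 2 | positive | 0.1003 to 0.3372 (correct) |

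The wrong interval is the complement of the right one: 1 − 0.3372 = 0.6628 and 1 − 0.1003 = 0.8997.

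**Step 3: no positives.** RESP then has one observed level, negative, and without a zero-count row that level is position 1 under every coding. For 0/50 the correct upper limit is 1 − 0.025^(1/50) = 0.0711, so the right interval is 0 to 0.0711 and the code returns 0.9289 to 1. For 0/80 the upper limit is 1 − 0.025^(1/80) = 0.0451, and the code returns 0.9549 to 1.

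**Step 4: another size, with 14/72 positive (19.4%).** Correct: 0.1106 to 0.3047. Negative level (58/72): 0.6953 to 0.8894.

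**Step 5: would it be noticed?** At 25/50 the two intervals are identical, so a test run on the SAP's headline scenario cannot reveal the problem. With n = 50, the negative-level interval contains the reported positive percentage for 22 to 28 positives and for no other count. At 22/50 (44%) the correct interval is 0.2999 to 0.5875 and the negative-level interval is 0.4125 to 0.7001. The latter still covers 44%, although both limits are about 11 percentage points too high. At 21/50 (42%) the negative-level interval, 0.4321 to 0.7181, no longer covers the estimate.

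**The case against.** The strongest reply is that this is template code. The dataset is a placeholder, RESP is generic, and 4.4.1, which governs, is clear about numerator, denominator and method. If positives are coded so that they sort first, the printed line is right whenever there is at least one positive. A reader might infer that the SAP's primary interval is wrong as written, or that the trial would report the complement of its endpoint. The documents do not support that, because they never give the coding of RESP.

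Three further points carry weight:
- The percentage of positives is to be reported with the interval, so 19.4% beside 69.5% to 88.9% would be questioned.
- The wrong interval is an exact complement, so the right one can be recovered.
- No positives at all is remote under the planning values: at 20% and n = 50 its probability is 0.8^50, about 0.000014. No test, margin or decision rule uses the interval.

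These points limit the consequence but do not dispose of the defect. Appendix 3 offers the line as the analysis code, and the labels the SAP itself uses (positive/negative, yes/no) sort the negative level first. The zero-positive failure needs no assumption about coding. The check by eye is weakest near 50%, the SAP's headline planning value.

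**Conclusion.** The point holds in conditional form. Appendix 3 selects the event by table position on an undefined variable. The result is the antibody-negative interval when the negative code sorts first, and under any coding when there are no positives. It is correct only when the positive code sorts first and at least one patient is positive.

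Where the selection goes wrong, each limit is replaced by one minus the opposite limit. At 20% positive with 50 patients this moves the interval from 10.0%–33.7% to 66.3%–90.0%. At exactly 50% nothing changes. Close to 50% the two intervals overlap heavily and the slip is hard to see.

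The conclusion rests on the PROC FREQ behaviour stated in the working and on the code being run without an ORDER= option or zero-weight rows, as printed. It is a programming specification to correct before the final analysis. The choice of endpoint and of the Clopper-Pearson method is not in question.

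**What to change.** In Appendix 3:

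1. State how RESP is coded and which value means at least one positive post-baseline screening result.
2. Select that level by its quoted formatted value, for example `binomial(level='1' exact)` or `binomial(level='Positive' exact)`, matching the coding in item 1.
3. Provide for 0/n: either add a positive row with zero weight and use a WEIGHT statement with the ZEROS option, or compute the exact limits directly from the beta quantiles.
4. Test the program on an asymmetric case such as 10/50 (expected 0.1003 to 0.3372) and on 0/50 (expected 0 to 0.0711), not only on 25/50.

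The level selection is a one-line change. The coding statement and the zero-count handling add a few more lines and a little data preparation. Endpoint, data collection and sample size are unaffected.
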